#### **5.14. Rescue Therapy**

A listing of all subjects receiving rescue therapy will be provided. The listing will include, but not be limited to, subject ID, treatment group, rescue therapy date, and dose.

#### **5.15. Exploratory Pharmacogenetic Analysis**

Pharmacogenetic analyses will be documented in a stand-alone PGx SAP and conducted by Lilly diabetes PGx statistics group or its designees.

#### **5.16. Interim Analyses**

A DMC (Data Monitoring Committee) will have access to unblinded data for their review(s). Only the DMC is authorized to evaluate unblinded interim safety analyses. The DMC will be composed of individuals internal and external to Lilly who are not part of the study team and will monitor the safety of U-500R administered CSII or MDI and may recommend changes to the protocol, including termination. The analysis plans for the DMC are specified in the DMC Charter.

## 6. Unblinding Plan

The purpose of this blinding and unblinding plan is to detail procedures in place to minimize bias while preparing for or conducting any summary or analysis of Study IBHD's data for DMC reports, trial level safety reports (TLSR), or CSRs. Additionally, this plan identifies who will be unblinded for the interim data analysis in support of the DMC meetings.

### 6.1. Creating the Blind: General Blinding Requirements

Study IBHD is a Phase 3b, multicenter, randomized, open-label, parallel clinical trial comparing U-500R administered by CSII (OmniPod U-500 system) to U-500R administered MDI in high-dose insulin-requiring subjects with T2DM. Treatment blinding of the investigators, subjects, and study site personnel is not feasible due to differences in the appearance and functionality of the delivery devices. To minimize bias, aggregate review of summary data by the study team (that is, clinical research physician/clinical research scientist (CRP/CRS) overseeing the global conduct of the study, statisticians, and statistical analysts) will remain blinded with respect to treatment assignment until after the final database is locked. Unblinding of the subject study treatment assignment may occur in the course of individual subject consultation between the investigator and the study team (principally between the investigator and the CRP/CRS) or during review of SAEs. No systematic unblinding of study treatment assignments will be solicited by the study team.

Besides the above discussion about treatment assignment, the following 5 case report forms (CRFs) will be blinded/scrambled to the study team (that is, CRP/CRS overseeing the global conduct of the study, statisticians, and statistical analysts) at an individual level, because they contain information which will lead to unblinding of treatment assignment:

- QS\_OMNI (OMNI1001)
- DE\_HAZ (OPHA1001)
- EX\_BASAL (EX1001\_F3)
- EX\_BOLUS (EX1001\_F4)
- EX\_RESCUE (EX1001\_F5)

### 6.2. Details of Maintaining the Blind

**For TLSR and DMC and the final data:** treatment assignments and the 5 CRF forms will remain blinded to study team as defined in Section 6.1.

- treatment assignments will be scrambled by data management group before raw data transfer
- the unblinded raw data for the 5 CRF forms together with other raw data will be transferred to: CLUWE/lillyce/qa/ly041001/b5k\_mc\_ibhd/prelock/data/raw/dm/edc

The study team as defined in Section 6.1 does not have access to this folder.

The DMC Statistical Analysis Center (SAC) statistician, who is outside of the study team, will scramble the QS\_OMNI (OMNI1001) and DE\_HAZ (OPHA1001) by reassigning the patient

IDs using a random patient list generated from all study patient IDs. The DMC SAC statistician will blind EX\_BASAL, by removing basal dose records (PAGE="EX1001\_F3"), which are the only information specific to CSII-arm subjects in this dataset. The bolus doses (EX\_BOLUS [EX1001\_F4]) and rescue doses (EX\_RESCUE [EX1001\_F5]) will be rounded to the nearest increment of 5.

Then the blinded data for each data transfer will be saved to:

- TLSR1: CLUWE/lillyce/qa/ly041001/b5k\_mc\_ibhd/safety\_review1/data/raw/shared
- TLSR2: CLUWE/lillyce/qa/ly041001/b5k\_mc\_ibhd/safety\_review2/data/raw/shared
- DMC: CLUWE/lillyce/qa/ly041001/b5k\_mc\_ibhd/dmc\_blinded1/data/raw/shared
- FINAL TEST DATA:  
CLUWE/lillyce/qa/ly041001/b5k\_mc\_ibhd/final/data/raw/shared

The study team statistician and analysts have access to this folder that contains blinded data

**For DMC:** summary of treatment assignments and the 5 CRF forms will be unblinded to the following who are all external to the study team:

- LRL Senior Management Designee
- SAC Statistician and DMC Secretary
- DMC Chairperson
- DMC Voting Members

The DMC SAC statistician will use the unblinded SDTM and ADaM data to generate TFL outputs, at the following locations respectively.

- SDTM folder:  
CLUWE/lillyce/qa/ly041001/b5k\_mc\_ibhd/dmc\_unblinded1/data/observed/restricted
- ADaM folder:  
CLUWE/lillyce/qa/ly041001/b5k\_mc\_ibhd/dmc\_unblinded1/data/analysis/restricted
- TFL folder:  
CLUWE/lillyce/qa/ly041001/b5k\_mc\_ibhd/dmc\_unblinded1/output/restricted

The study team does not have access to these folders.

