9.7. Transition to U-500R MDI

All subjects will administer U-500R MDI delivered TID (40:30:30 unless otherwise noted) during the transition period (Weeks 0-2). Transition to U-500R MDI will follow the criteria below in Table IBHD.9.3. Subjects will have their insulin adjusted weekly by the investigator using the algorithm from Section 9.8.2.1.

Table IBHD.9.3. Transition from entry insulin to U-500R MDI

Insulin Regimen (Screening)	HbA1c (Screening)	Mean SMBG (Screening to Week 0)	Conversion from Screening TDD to U-500R TID Dose
Insulin with or without U-500R	>8%	>183 mg/dL	1:1
Insulin with or without U-500R	>8%	≤183 mg/dL	Reduce TDD by 20%
Insulin with or without U-500R	≤8%	--	Reduce TDD by 20%
U-500R only	--	--	1:1

Abbreviations: HbA1c = hemoglobin A1c; SMBG=self-monitored blood glucose; MDI = multiple daily injections; TID= three times daily; TDD=total daily dose.

Subjects treated with U-100 and/or other concentrated insulin (with or without U-500R) at screening Visit 1 (Week -3) with HbA1c levels >8% and a mean SMBG (recorded prior to Visit 4 [Week 0]) value >183 mg/dL (corresponding to HbA1c value of >8.0% [estimated average glucose; Nathan et al. 2008]) at Visit 4 should be transitioned to U-500R using 1:1 dosage conversion.

Subjects treated with U-100 and/or other concentrated insulin (with or without U-500R) at screening Visit 1 (Week -3) with HbA1c levels >8% and a mean SMBG (recorded prior to Visit 4 [Week 0]) value ≤183 mg/dL (corresponding to HbA1c value of ≤8.0%) at Visit 4, should transition by reducing their U-500R TDD by 20%.

Subjects treated with U-100 and/or other concentrated insulin (with or without U-500R) at screening Visit 1 (Week -3) with HbA1c ≤8% should transition to U-500R at Visit 4 (Week 0) by reducing their U-500R TDD by 20%, regardless of SMBG value.

Subjects treated with U-500R insulin only at screening Visit 1 (Week -3) should transition to U-500R TID with proportion 40:30:30 using a 1:1 dosage conversion at Visit 4 (Week 0), regardless of HbA1c and/or SMBG. Those subjects already on U-500R TID at entry can continue their pre-entry U-500R TID proportions at the discretion of the investigator.

Investigators may also deviate from the proportion, if deemed necessary, for the safety or well-being of the subject (that is, due to a safety concern). Any major deviation from the recommended proportion must be discussed with Lilly CRP/CRS.

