9.8. Treatment Periods

9.8.1. CSII

The OmniPod U-500 system is designed to deliver U-500 insulin in insulin units without converting to U-100 insulin 'pump units' (Section [7.2](#)). Beginning at Visit 6 (Week 2), all CSII subjects will be instructed to change their OmniPod U-500 system Pod every 2 to 3 days (depending on TDD) during the treatment period. Subjects will be instructed to inspect Pod cannula insertion sites for signs of redness, swelling, or leakage and to respond to any CSII alarms (Bolderman et al. 2013).

For subjects randomized to CSII:

- The OmniPod U-500 system Pod should be filled in the clinic with U-500R during Visit 6.
- The highest 24-hour TDD from the past 3 days will be utilized for calculation of the CSII doses.
- 50% of the TDD will be basal split into 2 rates:
 - 2100 to 0600 hours 10% basal rate reduction
 - 0600 to 2100 hours for the calculated basal rate
- 50% of the TDD will be bolus split into the following ratio:
 - 40:30:30 (Section 9.8.1.3) for fixed bolus doses.
 - Suggested initial setting for insulin: CHO ratio should be programmed between 1:3 and 1:5.

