## 5.8. Protocol Deviations

A listing and summary of important protocol deviations will be generated for ARS for Group A+B and Group A (summary only). Important protocol deviations are defined as deviations from the study protocol that may compromise the data integrity and subjects' safety. Important protocol deviations are included in [Table IBHD.5.1](#) but these are not all-inclusive. Some situations not listed below may be decided on a case-by-case basis by the study team regarding whether to be considered as important and/or exclude subjects from the PP population. Subjects with one or more important protocol deviations that impact the primary efficacy outcome (per-protocol population exclusion flag [PPFLG]='Y' in [Table IBHD.5.1](#)) will be excluded from the PP population.

Table IBHD.5.1. Categorization of Important Protocol Deviations

Category	Sub-Category	Study Specific	Deviation Description	PPFLG	Methods of Identification
Informed Consent	Informed Consent Not Obtained	Lack of patient signature for main protocol	1. Issues with informed consent: lack of patient signature (main protocol )	Y	CRF data indicate the Study ICD date missing for main study.
Informed Consent	Improper Consent	NA	2. Issues with informed consent: lack of PI signature, date signed is after V1, lack of patient signature for CGM, revised ICD not signed (main protocol and CGM addendum)	N	Monitoring
Eligibility	Inclusion/Exclusion	No T2DM	3. No confirmation of T2DM	Y	Medical history CRF data indicate missing record
Eligibility	Inclusion/Exclusion	No T2DM	4. Not diagnosed with T2DM	Y	Monitoring
Eligibility	Inclusion/Exclusion	TDD out of range at study entry	5. TDD is out of range (Inclusion range is >200U or ≤600U) at Visit 1	N	Data Management Reports and Monitoring
Eligibility	Inclusion/Exclusion	TDD out of range at study entry	6. 4.TDD is out of range (Inclusion range is >200U or ≤600U) at Visit 4	Y	Data Management Reports and Monitoring
Eligibility	Inclusion/Exclusion	HbA1c out of the range at study entry	7. HbA1c out of the range at study entry: (Inclusion range ≥7.5% and ≤12.0) at Visit 1	Y	GLS data
Eligibility	Inclusion/Exclusion	Age out of range	8. Age out of range (>85 or <18 yrs)	N	Edits or monitoring
Eligibility	Inclusion/Exclusion	BMI out of range at study entry	9. BMI out of range at study entry: (Inclusion range ≥25kg/m  and ≤50kg/m  ) at Visit 1	Y	Edits

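### Rounding bolus doses to the nearest 5 does not mask the arm: the CSII bolus total falls to about half after Visit 6, so almost all subjects with later dose records can be identified

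*SAP*

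**What the plan says.** Sites cannot be blinded in this open-label trial. SAP 6.1 and Protocol 9.10 therefore keep the sponsor's study team (CRP/CRS, statisticians and statistical analysts) blinded in aggregate review until final lock. SAP 6.1 names five case report forms, EX_BOLUS among them, to be masked to that team for each subject "because they contain information which will lead to unblinding of treatment assignment".

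SAP 6.2 then describes the masking form by form:
- QS_OMNI and DE_HAZ are scrambled by reassigning patient "IDs using a random patient list generated from all study patient IDs".
- EX_BASAL is masked "by removing basal dose records".
- EX_BOLUS and EX_RESCUE keep their dose values, which "will be rounded to the nearest increment of 5".

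The masked files serve the two trial-level safety reviews, the blinded DMC transfer and the final test data. On access, SAP 6.2 says: "The study team statistician and analysts have access to this folder that contains blinded data".

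Two dosing rules in the protocol matter here. Section 9.7 puts both arms on one regimen at first: "All subjects will administer U-500R MDI delivered TID (40:30:30 unless otherwise noted) during the transition period (Weeks 0-2"). Section 9.8.1 then changes the CSII arm at Visit 6: "50% of the TDD will be bolus split into the following ratio", with the other half given as basal. The MDI arm stays all bolus.

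**The concern.** Rounding to 5 deals with one clue, the dose grid: CSII doses are set to 0.25 U and MDI doses to 5 U. It leaves a larger clue in place. Each subject provides an all-bolus total in Weeks 0-2. After Visit 6 the CSII total should halve and the MDI total should not. Deleting the basal records makes the fall look like a genuine loss of half the dose. If the rows still carry true patient IDs, anyone with the file can read off the arm by comparing two visits.

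What is at stake is a property that the plan claims for itself. SAP 6.1 accepts unblinding of individual subjects in consultations and SAE review, and says that no systematic unblinding will be solicited. A shared file that reveals nearly all arms is a different matter. Under SAP 5.8, situations not in the deviation table "may be decided on a case-by-case basis by the study team", including whether a subject leaves the per-protocol set. That set supports the noninferiority conclusion.

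**Working it through.** The plan gives no figure for how well the masking works, so there is none to reproduce. The check applies the protocol's dosing rules and then the SAP's mask.

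**Inputs**
- Entry TDD above 200 and up to 600 U (Protocol 8.1). The 20% transition reduction in Table IBHD.9.3 can take this to about 0.8 × 200 = 160 U, so the range checked is 160 to 600 U.
- Weeks 0-2, both arms: split 40:30:30 (9.7), rounded to 5 U (9.8.2).
- CSII from Visit 6: half of TDD as bolus, split 40:30:30 (9.8.1), rounded to 0.25 U (Table IBHD.9.5 note), then to 5 U (SAP 6.2).
- Largest MDI reductions: -10 U per dose below 400 U TDD or -20 U per dose from 400 U (Table IBHD.9.6), or 20% off the corresponding dose for low glucose (its footnote b), here applied to all three doses.

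**Formulas**, with M the daily total in Weeks 0-2:
- CSII ratio = (sum of three masked CSII boluses) / M
- MDI table ratio = (M - 30)/M below 400 U, (M - 60)/M from 400 U
- MDI low-glucose ratio = (sum of three doses × 0.8, each rounded to 5) / M

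| TDD | Doses, Weeks 0-2 | M | CSII bolus, masked | CSII ratio | MDI table ratio | MDI low-glucose ratio |
|---|---|---|---|---|---|---|
| 160 | 65/50/50 | 165 | 85 | 0.515 | 0.818 | 0.788 |
| 200 | 80/60/60 | 200 | 100 | 0.500 | 0.850 | 0.825 |
| 250 | 100/75/75 | 250 | 130 | 0.520 | 0.880 | 0.800 |
| 300 | 120/90/90 | 300 | 150 | 0.500 | 0.900 | 0.783 |
| 400 | 160/120/120 | 400 | 200 | 0.500 | 0.850 | 0.800 |
| 480 | 190/145/145 | 480 | 235 | 0.490 | 0.875 | 0.792 |
| 600 | 240/180/180 | 600 | 300 | 0.500 | 0.900 | 0.800 |

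Over every whole-unit TDD from 160 to 600, the CSII ratio runs from 0.47 to 0.52. The lower of the two MDI ratios runs from 0.77 to 0.83. The ranges do not overlap.

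**Stress tests on the CSII side**
- Largest upward bolus titration (Table IBHD.9.5: +7.5 or +15 U per dose): ratio 0.58 to 0.65 at the TDDs checked, still below the MDI floor.
- Correction boluses at all three meals (9.8.1.1: 1:10 below 400 U, 1:5 from 400 U, target 100 mg/dL). At TDD 200 and glucose 250 mg/dL, each meal gains (250 - 100)/10 = 15 U, so the ratio is (100 + 45)/200 = 0.725. Over the TDDs checked the ratio is 0.65 to 0.79 at 250 mg/dL and 0.70 to 0.88 at 300 mg/dL. Overlap with MDI is possible only here.
- Simulation, 200,000 subjects per arm. Assumed: uniform TDD 160-600 U, pre-meal glucose mean 180 and SD 40 mg/dL, dose noise 0 to 10%, CSII share fixed at 50%, MDI titrated by the table, cut at 0.75 or 0.80. The worst settings misclassified 0.4% of CSII and 0.001% of MDI subjects. These rates depend on the assumptions; the ranges in the table do not.

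**Timing.** SAP 5.10 uses the highest bolus total from the 3 days before each visit. If EX_BOLUS holds those days, the Visit 6 record is still pre-switch and the fall first shows at Visit 7.

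**The case against.** Several counter-arguments have force.

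- A reader might infer that every subject's arm is exposed. The documents do not support that. Both arms have the same regimen until Visit 6, so a subject with no later dose record shows nothing. The 50% split is also a starting rule: carbohydrate-based boluses, corrections and investigator deviations can move it.
- A reader might infer that EX_BOLUS certainly keeps true IDs and that the whole study team sees it. The SAP states neither. Retained IDs are inferred because reassignment is described for two forms only. Access is stated for the statistician and analysts; the CRP/CRS is not named. The inference is reasonable, since rounding would add little if IDs were already scrambled, and SAP 6.1 counts statisticians and analysts as study team.
- EX_RESCUE gets the same rounding, but the halving argument does not extend to it. Suggested starting rescue doses are 10% of TDD for MDI and 5% to 10% for CSII (Protocol 9.9.1), so they overlap.
- The harm is bounded. The primary test uses all randomized Group A subjects and centrally assayed HbA1c. Per-protocol is supportive, and SAP Table IBHD.5.1 fixes the exclusion flag for 61 listed deviations. No alpha, power or sample size is affected. Computing each subject's dose ratio would also go against the stated intent not to unblind systematically.
- Other data can reveal the arm. Deviation item 46 concerns staying on CSII or MDI, and item 60 mentions Pod dispensing. Device relatedness of adverse events and infusion-site changes are specific to the pump, and none is tied to the five masked forms. Masking EX_BOLUS alone would not guarantee a complete blind.

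These points limit the scope and the consequence. None of them makes rounding to 5 hide a fall by half.

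**Conclusion.** The point holds in a limited form. As SAP 6.2 is written, the masking of EX_BOLUS does not deliver the subject-level masking promised in SAP 6.1. The visible CSII total falls to 0.47-0.52 of its earlier value, against a one-step MDI floor of about 0.77-0.83. The study statistician and analysts could infer the arm of almost all subjects with a dose record after Visit 6.

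This rests on four assumptions: the rows keep true IDs; CSII subjects start near the 50% split; the MDI arm has no more than one reduction between the two records compared; and missed-meal days are set aside by taking the 3-day maximum. Two successive 20% reductions in an MDI subject would give about 0.8 × 0.8 = 0.64. That is still above 0.52 but within the range of a fully up-titrated CSII subject.

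It would be going too far to infer that the primary result is at risk. The exposure is to case-by-case deviation and per-protocol decisions, and to the accuracy of a later statement that the sponsor's team was blinded. It merits correction because the repair is cheap and the rule as written does not do its job.

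**What to change.** In the safety-review, blinded-DMC and final test transfers, reassign patient IDs in EX_BOLUS in the way already described for QS_OMNI and DE_HAZ, or withhold its dose values until database lock. If IDs are already reassigned in practice, one sentence in SAP 6.2 settles the matter. EX_RESCUE can be handled the same way for consistency, although no unblinding by halving is shown for it.

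The DMC statistician outside the study team already runs this kind of scramble, so the extra work is small. No subject, endpoint or error rate is affected. The cost is that dose tables and dose-to-event linkage are programmed on scrambled data until lock. If last-dose dates or exposure are taken from this form (an assumption; the SAP does not name their source), on-treatment flags in the blinded reviews would also be provisional. In that case, keeping true IDs and dates but withholding the dose values is the better option.

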## 7. CGM Addendum

Unless otherwise specified, all discussions in this section are within the context of the CGM addendum only. Subjects who choose to participate in Protocol Addendum IBHD(1) will sign an addendum-specific informed consent form (ICF). The commercial CGM device (Dexcom G4 Platinum) that will be used for this addendum is labeled to collect data for 7 consecutive days. These subjects will be asked to perform CGM on 3 occasions for up to 7 days per occasion as indicated in the Study Schedule. Continuous glucose monitoring should occur during the week prior to Visit 4 (Week 0), Visit 13 (Week 14), and Visit 17 (Week 26).

### 7.1. Addendum Objectives

#### 7.1.1. Primary Objective

The primary objective of this addendum is to compare glycemic control change from baseline to end of treatment period of within-day glucose variability as measured by mean daily SD of the interstitial glucose measurements between CSII and MDI.

#### 7.1.2. Secondary Objectives

The secondary objectives for the CGM addendum are:

- 1) To compare glycemic control change from baseline to endpoint of the treatment period between CSII and MDI as assessed by CGM based on mean daily AUC and percentage of time:
  - $\leq 70$  mg/dL
  - $\leq 50$  mg/dL
  - $\geq 180$  mg/dL
  - $\leq 70$  mg/dL during the nocturnal period between midnight and 0600 hours
  - $\leq 50$  mg/dL during the nocturnal period between midnight and 0600 hours
  - $>70$  mg/dL to  $\leq 120$  mg/dL
- 2) To compare the low blood glucose index (LBGI) and high blood glucose index (HBGI) during the nocturnal period defined as midnight to 0600 hours and during a 24-hour period between CSII and MDI at end of treatment period
- 3) To compare the combined BG risk index (sum of the LBGI and HBGI) during the nocturnal period defined as midnight to 0600 hours and during a 24-hour period between CSII and MDI at end of treatment period
- 4) To evaluate the insulin-on-board (IOB, 6- or 8-hour) pump settings by analysis of mean glucose AUC between bolus doses at breakfast and lunch and between bolus doses at lunch and dinner, respectively, for CSII treatment at end of treatment period
- 5) To evaluate optimal bolus timing (15 or 30 minutes prior to meal) response by analysis of mean glucose AUC for 4 hours after the start of the meal at end of treatment period

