7.1.2. Type 2 Diabetes Lifestyle Counseling

Per the study schedule ([Attachment 1](#)), qualified medical staff will provide diabetes management counseling including diet, exercise, and education about the signs, symptoms, and treatment of hypoglycemia, should it occur. Subjects should continue their usual exercise habits and generally follow stable meal plans (consistent meal size and time of day) throughout the course of the study. Instruction on how to assess CHO content and caloric content of meals may be incorporated into the counseling. Dietary counseling may be reviewed throughout the study as needed. Subjects are not to initiate a weight loss program during the trial.

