9.8.1.3. CSII Bolus Dosing

Subjects should bolus 30 minutes prior to meals except for a subset of the subjects in the CGM addendum who will be assigned to bolus 15 minutes prior to meals.

Subjects should be encouraged to eat a bedtime snack (Extend Bar 21 gm CHO or equivalent) without administering a bolus for the snack. **Note:** If the subject has an allergy or intolerance to the Extend Bar, then the subject may substitute a bedtime snack between 15 and 25 grams CHO.

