## 7.3. Analytic Variables

A third party organization (TPO) will collect and compile the CGM data. Besides the CGM raw data, the TPO will also provide the analytic variables for each patient as follows:

- daily SD of the CGM glucose measures
- daily amplitude of glycemic excursion (MAGE) index and continuous overall net glycemic action (CONGA)
- daily AUC and percentage of time when glucose measures are:
  - $\leq 70$  mg/dL
  - $\leq 50$  mg/dL
  - $\geq 180$  mg/dL
  - $\leq 70$  mg/dL during the nocturnal period between midnight and 0600 hours
  - $\leq 50$  mg/dL during the nocturnal period between midnight and 0600 hours
  - $> 70$  mg/dL to  $\leq 120$  mg/dL
- daily LBGI, HBGI, and the combined BG risk index (sum of the LBGI and HBGI) during the nocturnal period (defined as midnight to 0600 hours) and during a 24-hour period
- daily AUC between bolus doses at breakfast and lunch and daily AUC between bolus doses at lunch and dinner, respectively
- daily AUC for 4 hours after the start of each meal

MAGE is the mean of the differences between consecutive peaks and nadirs in BG, provided that the absolute value of difference was greater than the SD (Service et al. 1970). CONGA is the SD of the difference between the current and previous observations and measures the overall intra-day variation of glucose recorded by CGM (McDonnell et al. 2005).

The LBGI (Kovatchev et al. 2005) has been developed to quantitate both frequency and severity of hypoglycemia. The LBGI has been validated as a predictor of severe hypoglycemia (Kovatchev et al. 2003; Kovatchev et al. 1998), which is a SAE and could result in coma or death if unrecognized and untreated. The HBGI quantifies both frequency and severity of hyperglycemia (Kovatchev et al. 2005) and has been related to HbA1c and risk for hyperglycemia (Kovatchev et al. 2003). Additionally, the LBGI and HBGI both have a high sensitivity to changes in glycemic profiles and control (Kovatchev et al. 2002). The LBGI and HBGI will be derived values.

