## 7.4. A Priori Statistical Methods

Baseline characteristics will be summarized by treatment arm. Means will be analyzed using an analysis of variance model. Proportions will be analyzed using Fisher's exact test.

The primary objective measure is mean daily SD calculated as the mean of the optimal values for each visit. An MMRM model will be used to analyze the actual measurements and change from baseline of the continuous dependent variables. The model will include fixed effects such as treatment, weeks on treatment (considered as categorical variable), the interaction between treatment and weeks, and the stratification factors. Subject will be considered as a random effect. The corresponding baseline values will be included as a covariate.

For the MMRM model, the Kenward-Roger approximation will be used to estimate denominator degrees of freedom. An unstructured covariance matrix will be used to model the within-subject errors. If the unstructured covariance configuration results in a lack of convergence, then the following variance-covariance matrix will be used (in order) until one converges:

Heterogeneous Toeplitz; Heterogeneous First Order Autoregressive; Heterogeneous Compound Symmetry; Toeplitz; First Order Autoregressive; Compound Symmetry. If all variance-covariance matrices selected fail to converge, Variance Components will be used as the next attempt at convergence.

If the model still does not converge after changing to different covariance structures, then the stratification factors will be removed from the model. If the model still does not converge, then an ANCOVA analysis which only includes baseline and the 26-week values will be performed.

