The similar variable calculation method and MMRM approach will be used for all other secondary objectives. Model specifications, such as fixed effects, covariates, and repeated measurement structures need to be carefully adjusted according to the specific objectives and measurements. For Secondary Objective 4, only those subjects assigned to CSII arm will be analyzed; therefore, the treatment effect and its interactions with other effects will be removed from the model. For Secondary Objective 5, the interaction between optimal bolus timing (15 or 30 minutes prior to meal) and treatment will be added into the MMRM model; the interaction between optimal bolus timing and weeks will also be added. Depending on the model convergence situation, the interaction between treatment and weeks may be removed.

Other measures of variability of the interstitial glucose measurements may be analyzed as sensitivity analyses (for example, MAGE index and CONGA).

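### CGM Objective 4 compares the 6- and 8-hour pump settings on an AUC whose window is set by each subject's meal spacing; normalise it for time and name the setting in the model

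*SAP*

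**What the plan says.** SAP 7.1.2 sets Objective 4 for CSII subjects only: the 6- or 8-hour IOB setting is evaluated at the end of treatment "by analysis of mean glucose AUC between bolus doses at breakfast and lunch and between bolus doses at lunch and dinner". The variable that the third party will supply, in SAP 7.3, is "daily AUC between bolus doses at breakfast and lunch and daily AUC between bolus doses at lunch and dinner, respectively". For Objective 5 (bolus timing) the same list gives "daily AUC for 4 hours after the start of each meal", which is a window of fixed length.

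SAP 7.4 describes the primary CGM variable as "mean daily SD calculated as the mean of the optimal values for each visit". SAP 7.4 then adds: "The similar variable calculation method and MMRM approach will be used for all other secondary objectives".

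The base model in SAP 7.4 has treatment, week, treatment by week, the stratification factors and the baseline value. For Objective 4, because only CSII subjects are analysed, "therefore, the treatment effect and its interactions with other effects will be removed from the model". Nothing is added by name. For Objective 5, interactions of bolus timing with treatment and with week are added by name.

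The length of the interval is tied to meals. Protocol 9.8.1.3 states: "Subjects should bolus 30 minutes prior to meals except for a subset of the subjects in the CGM addendum", the exception being a 15-minute lead. Protocol 7.1.2 asks subjects to "generally follow stable meal plans (consistent meal size and time of day", but sets no clock times or common spacing. Protocol 9.8.1.1 has CSII subjects hold the bolus when a meal is skipped.

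**The concern.** An AUC over an interval is the mean glucose in that interval multiplied by its length. If the length differs between subjects, the endpoint measures meal spacing as well as glucose. The IOB comparison is between subjects, so differences in habitual spacing enter it directly. Two subjects with the same control can get different values, and a subject with lower glucose and a longer gap can score higher than one with higher glucose and a shorter gap.

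The second part is the model. IOB setting is the only factor that Objective 4 asks about. Once treatment and its interactions are removed, the terms stated by name are week, the stratification factors and baseline. None of these estimates 8 hours versus 6 hours.

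What is at stake is whether a small exploratory comparison can be read as a statement about glucose. No confirmatory result depends on it.

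**Working it through.** **The plan's own figure.** SAP 7.2 wants 20 completers per arm at 25% dropout: 20 / (1 − 0.25) = 26.7, rounded up to 27 per arm and 54 in total. This reproduces the stated numbers. Objective 4 therefore has about 20 CSII completers. The split between 6 and 8 hours is not given.

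**Step 1: what raw AUC measures.** AUC = G × L, with G the mean glucose over the interval and L its length. The glucose and interval values here are illustrations; none comes from the documents.

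- Same glucose, different gap: 160 × 5 = 800 and 160 × 6 = 960 mg·h/dL, a 20% difference with identical control.
- Reversed ranking: 180 × 4 = 720, but 140 × 6 = 840.
- Half an hour more at 160 mg/dL adds 0.5 × 160 = 80 mg·h/dL. Over a 5-hour gap that equals a rise of 80 / 5 = 16 mg/dL.

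**Step 2: cost in variance.** If G and L are independent, with coefficients of variation CVg and CVt, the relative variance of G × L is CVg² + CVt² + CVg²·CVt². Divided by CVg², the ratio to mean glucose alone is 1 + CVt²/CVg² + CVt². With CVg = 20% (assumed):

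- CVt = 10%: 1 + 0.25 + 0.01 = 1.26
- CVt = 15%: 1 + 0.5625 + 0.0225 = 1.585
- CVt = 20%: 1 + 1 + 0.04 = 2.04

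These are crude between-subject variances, with no baseline adjustment.

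**Step 3: what that does to a comparison of this size.** Assumptions: 10 subjects per setting, a true difference of 20 mg/dL, mean glucose 160 mg/dL, mean gap 5 hours. SD(AUC) = √(L²·sdG² + G²·sdL² + sdG²·sdL²). For example, with sdG = 25 mg/dL and sdL = 0.5 h, √(15,625 + 6,400 + 156) = 148.9, against 5 × 25 = 125 if the gap were constant. Two-sided 5% power by the normal approximation:

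| Glucose SD (mg/dL) | Time-averaged | Raw, interval SD 0.25 h | 0.5 h | 0.75 h | 1.0 h |
|---|---|---|---|---|---|
| 25 | 0.43 | 0.40 | 0.32 | 0.25 | 0.19 |
| 35 | 0.25 | 0.24 | 0.21 | 0.18 | 0.15 |

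The loss is small if subjects space their meals alike and large if they do not. Power is low in every cell.

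**Step 4: which kind of mean is intended.** The mean in Objective 4 could be over time within the interval or over days within the visit. SAP 7.3 lists a plain daily AUC. SAP 7.4 describes the primary variable as a mean of values for each visit and carries a similar calculation to the secondary objectives. Objective 5 uses the same term for a window of fixed length, where time-averaging would change nothing. The text therefore points to averaging over days, without settling it.

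**The case against.** The strongest reply has four parts.

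*The endpoint may already be time-averaged.* The wording of Objective 4 allows that reading, and the addendum protocol, which is not among the documents, may define the variable. But SAP 7.3 states what the third party is to deliver, and it states no division. The ambiguity stands as a reason to write one sentence, not as an answer.

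*The model is not closed.* A reader might infer that Objective 4 has been given a model that excludes the IOB setting and so cannot answer its question. The documents do not support that. SAP 7.4 introduces its fixed effects as examples, and just before the Objective 4 text it says that fixed effects must be adjusted to each objective. The term is implicit, not ruled out. What remains is that the factor of interest is unnamed here while its counterpart in Objective 5 is named.

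*Other features of the design reduce the noise.* Subjects are asked to keep regular meal times, each CGM occasion lasts up to 7 days, and the baseline value is a covariate. Regular meals and averaging over days reduce variation within a subject; they do not give subjects a common spacing. Baseline adjustment could absorb part of the habitual difference where a baseline inter-bolus AUC exists. It may not always exist: the baseline recording precedes Visit 4, CSII starts at Week 2, and Protocol 8.1 admits basal-only and premixed regimens.

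*Dividing by time is only a partial cure.* A short interval mostly captures the post-meal peak and a long one adds the later decline, so mean glucose still depends on length. This is correct, and it is a reason to offer a fixed window as the alternative. Days with a held bolus have no interval and would drop out anyway, so they add little to the concern beyond a need to say so.

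**Conclusion.** The point holds as a low-priority correction to an exploratory objective. As stated, the Objective 4 endpoint mixes meal spacing with glucose, the plan's own Objective 5 shows a form that avoids this, and the IOB term should be named.

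The size is uncertain. The ratio of 1.26 to 2.04 rests on an assumed glucose variation of 20% and interval variation of 10 to 20%, independent of each other, before baseline adjustment. A reader might take the middle case, where 1 − 1/1.585 is about 37%, as the information lost, or conclude that spacing would swamp any effect. Neither is established: no variance is given in the documents, the planned model adjusts for baseline, and in the illustration the raw endpoint falls well behind only when gaps vary widely between subjects. The comparison is weak under either definition, because SAP 7.2 does not size the addendum for power.

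Nor do the documents show that spacing biases the comparison. They do not say how subjects are assigned to 6 or 8 hours. If assignment is random, spacing mainly adds noise; if not, it could also bias. The primary analysis, the key secondary hypotheses and alpha are unaffected.

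**What to change.** In SAP 7.3, define the Objective 4 variable in one of two ways:

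- each inter-bolus AUC divided by its elapsed time, using only days on which both boluses were given, then averaged over days within the visit; or
- AUC over a fixed window after the bolus, with the length set in advance, in the manner of Objective 5. This also removes the remaining dependence of mean glucose on interval length.

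State what is done on days with a held bolus and for subjects who have no meal boluses at baseline.

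In SAP 7.4, name IOB setting (6 or 8 hours) and IOB-by-week as fixed effects for Objective 4. State how the setting is assigned and how many subjects are planned for each, or refer to the addendum protocol if it says so.

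The cost is one derivation and one model line. The third party needs the bolus times in any case to compute the AUCs now listed. Sample size and study procedures do not change.
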